11.0 Safety Analysis

11.1 General Considerations

Safety data will be summarized using the safety population.

11.2 Analysis of Adverse Events

Adverse events will be coded using the Medical Dictionary for Regulatory Activities (MedDRA). The actual version of the MedDRA coding dictionary will be noted in the clinical study report.

11.2.1 Treatment-Emergent Adverse Events

Treatment-emergent adverse events are defined as any adverse event (AE) with an onset date that is after the first dose of study drug and no more than 30 days after the last dose of study drug. Events where the onset date is the same as the study drug start date are

ABT-493/ABT-530 M13 596 Statistic

ABT-493/ABT-530 M13-596 – Statistical Analysis Plan Version 1.0 – 27 October 2016

assumed to be treatment-emergent. If an incomplete onset date was collected for an adverse event, the event will be assumed to be treatment-emergent, unless there is other evidence that confirms that the event was not treatment-emergent (e.g., the event end date was prior to the study drug start date).

11.2.2 Tabulations of Treatment-Emergent Adverse Events

The number and percentage of subjects will be tabulated by primary MedDRA System Organ Class (SOC) and preferred term (PT). The system organ classes will be presented in alphabetical order, and the preferred terms will be presented in alphabetical order within each system organ class.

Adverse Event Overview

An overview of AEs will be presented consisting of the number and percentage of subjects experiencing at least one event for each of the following AE categories:

- Any treatment-emergent adverse event;
- Treatment-emergent adverse events with a "reasonable possibility" of being related to DAAs (ABT-493/ABT-530);
- Treatment-emergent adverse events of Grade 3 or higher;
- Serious treatment-emergent adverse events;
- Serious treatment-emergent adverse events with a "reasonable possibility" of being related to DAAs (ABT-493/ABT-530);
- Treatment-emergent adverse events leading to discontinuation of study drug;
- DAA-related treatment-emergent adverse events leading to discontinuation of study drug;
- Treatment-emergent adverse events of Grade 3 or higher with a "reasonable possibility" of being related to DAA (ABT-493/ABT-530);
- Serious treatment-emergent adverse events leading to discontinuation of study drug;
- Treatment-emergent adverse events leading to interruption of study drug;
- Treatment-emergent adverse events leading to death;

• Deaths.

Adverse Events by SOC and PT

Subjects reporting more than one AE for a given PT will be counted only once for that term (most severe/highest grade incident for the severity tables and most related incident for the relationship tables). Subjects reporting more than one AE within an SOC will be counted only once for that SOC. Subjects reporting more than one AE will be counted only once in the overall total.

The following summaries of AEs by SOC and PT will be generated:

- Treatment-emergent adverse events;
- Treatment-emergent adverse events with a "reasonable possibility" of being related to DAAs (ABT-493/ABT-530);
- Serious treatment-emergent adverse events;
- Serious treatment-emergent adverse events with a "reasonable possibility" of being related to DAAs (ABT-493/ABT-530);
- Grade 3 or higher treatment-emergent adverse events;
- Treatment-emergent adverse events of Grade 3 or higher with a "reasonable possibility" of being related to DAAs (ABT-493/ABT-530);
- Treatment-emergent adverse events leading to discontinuation of study drug;
- DAA-related treatment-emergent adverse events leading to discontinuation of study drug;
- Serious treatment-emergent adverse events leading to discontinuation of study drug;
- Treatment-emergent adverse events leading to interruption of study drug;
- Treatment-emergent adverse events leading to death.

A listing of treatment-emergent adverse events grouped by body system and preferred term with subject numbers will be created.

Adverse Events by PT

The number and percentage of subjects experiencing treatment-emergent adverse events will be tabulated according to PT and sorted by overall frequency. Similar summaries will be provided for Grade 3 or higher treatment-emergent adverse events, DAA-related treatment-emergent adverse events, DAA-related Grade 3 or higher treatment-emergent adverse events.

Adverse Events by Maximum Severity Grade Level

Treatment-emergent adverse events and DAA-related treatment-emergent adverse events will be summarized by maximum severity grade level of each preferred term. Each adverse event will be assigned a grade level (Grade 1, 2, 3, 4, or 5) by the investigator. If a subject has an AE with unknown severity, then the subject will be counted in the severity grade level category of "unknown," even if the subject has another occurrence of the same event with a severity present. The only exception is if the subject has another occurrence of the same AE with the highest grade level (Grade 5). In this case, the subject will be counted under the "Grade 5" category.

Adverse Event by Maximum Relationship

Treatment-emergent adverse events also will be summarized by maximum relationship of each preferred term to study drug (DAA), as assessed by the investigator. If a subject has an adverse event with unknown relationship, then the subject will be counted in the relationship category of "unknown," even if the subject has another occurrence of the same event with a relationship present. The only exception is if the subject has another occurrence of the same adverse event with a relationship assessment of "Reasonable Possibility." In this case, the subject will be counted under the "Reasonable Possibility" category.

Other Adverse Events

The number and percentage of subjects experiencing at least one treatment-emergent adverse event in the search defined below by Product MedDRA Query (PMQ) will be

presented overall and by SOC and PT. In addition, a listing of treatment-emergent adverse events for subjects meeting the search criterion will be provided.

"Hepatic Decompensation and Hepatic Failure" (PMQ)

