6.1.3 Relationship to Study Drug

The investigator will use the following definitions to assess the relationship of the adverse event to the use of study drug:

Reasonable Possibility	An adverse event where there is evidence to suggest a causal relationship between the study drug and the adverse event.
No Reasonable Possibility	An adverse event where there is no evidence to suggest a causal relationship between the study drug and the adverse event.

For causality assessments, events assessed as having a reasonable possibility of being related to the study drug will be considered "associated." Events assessed as having no reasonable possibility of being related to study drug will be considered "not associated." In addition, when the investigator has not reported a causality or deemed it not assessable, AbbVie will consider the event associated.

For serious adverse events, if an investigator's opinion of relatedness is "no reasonable possibility of being related to study drug" an "other" cause of event must be provided by the investigator.

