8.1.5.1 Adverse Events

[figure not shown]
Adverse events will be coded using the Medical Dictionary for Regulatory Activities (MedDRA). The number and percentage of subjects with treatment-emergent adverse events (i.e., any event that begins or worsens in severity after initiation of study drug through 30 days post-study drug dosing) will be tabulated by primary MedDRA System Organ Class (SOC) and preferred term (PT). The tabulation of the number of subjects with treatment-emergent adverse events by severity grade and relationship to study drug also will be provided. Subjects reporting more than one adverse event for a given MedDRA preferred term will be counted only once for that term using the most severe grade for the severity grade table and the most related for the relationship to study drug tables. Subjects reporting more than one type of event within a SOC will be counted only once for that SOC.

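### SAP 11.2.2 tabulates missing causality as unknown where protocol 6.1.3 treats it as associated, so drug-related adverse event counts can be understated if any assessments are missing

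*SAP*

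**What the plan says.** **Causality.** Protocol section 6.1.3 gives the investigator two choices, reasonable possibility or no reasonable possibility, and equates the first with association: "events assessed as having a reasonable possibility of being related to the study drug will be considered 'associated". It then covers the case with no usable assessment: "when the investigator has not reported a causality or deemed it not assessable, AbbVie will consider the event associated". Protocol section 8.1.5.1 fixes how repeated events within a preferred term are counted: "using the most severe grade for the severity grade table and the most related for the relationship to study drug tables".

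SAP section 11.2.2 plans a table "summarized by maximum relationship of each preferred term to study drug (DAA), as assessed by the investigator". Its rule for missing data begins "If a subject has an adverse event with unknown relationship, then the subject will be counted in the relationship category of" *unknown*, and this applies even if another occurrence has a relationship recorded. The one exception is another "occurrence of the same adverse event with a relationship assessment of 'Reasonable Possibility", in which case the subject is counted as related.

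**Severity.** The same SAP section says, under the tables by system organ class and preferred term, that the highest grade and the most related incident are used. For the maximum-severity tables it adds: "If a subject has an AE with unknown severity, then the subject will be counted in the severity grade level category of" *unknown*. Here only a known Grade 5 for the same event takes precedence.

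**Declared changes.** SAP section 12.1 lists two differences from the protocol, one on resistance analyses and one on efficacy subgroups. Adverse event conventions are not among them.

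**The concern.** Under the protocol, an event with no causality assessment belongs with the drug-related events. Under the SAP, it goes to a separate class that is neither related nor unrelated. The two documents therefore give different counts from the same data, and nothing tells the reader which convention was intended.

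Safety is part of the primary objective. The study has a single arm of about 90 subjects, so the absolute counts of related and severe events carry the safety description. The SAP's causality rule can lower the related count relative to the protocol's rule, but it can never raise it.

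The severity rule raises a smaller question. A table of maximum severity discards a grade that was actually observed because another occurrence of the same term has none.

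**Working it through.** No power, alpha or sample-size figure is involved, so there is no stated result to reproduce. The check applies each rule to one subject and one preferred term.

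**Step 1: causality.** RP is reasonable possibility, NRP is no reasonable possibility, U is not reported or not assessable. The SAP column follows section 11.2.2. The protocol column applies 6.1.3 (U counts as associated) and then 8.1.5.1 (most related occurrence).

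| Occurrences | SAP | Protocol |
|---|---|---|
| U | unknown | associated |
| U, U | unknown | associated |
| NRP, U | unknown | associated |
| RP, U | related | associated |
| NRP, NRP | not related | not associated |

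The rules differ whenever a U occurs without a known RP. The difference always runs the same way: the subject leaves the related row and appears as unknown.

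**Step 2: the other drug-related tables.** The overview and the tables by system organ class and preferred term define related events by reasonable possibility. The preferred-term and maximum-severity summaries use the label DAA-related. The SAP states no rule that maps an unknown relationship into either group. On a literal reading a U event is in neither, but the SAP does not say so explicitly.

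**Step 3: severity.** U now means ungraded.

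| Occurrences | SAP maximum-severity table | Highest known grade | Has a known Grade 3+ event |
|---|---|---|---|
| 1, U | unknown | 1 | no |
| 2, U | unknown | 2 | no |
| 3, U | unknown | 3 | yes |
| 4, U | unknown | 4 | yes |
| 5, U | 5 | 5 | yes |
| U, U | unknown | unknown | no |

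Four combinations change. In the two that involve a known Grade 3 or 4, the subject still has at least one such event. That subject therefore still counts in the Grade 3 or higher lines of the overview and in the separate Grade 3 or higher tables, for which no unknown override is written.

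**Step 4: size.** If k subjects are affected and about 90 are treated (planned enrolment, protocol 8.2 and SAP 4.3), a table row shifts by at most 100 × k/90 points:

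- k = 0: 0
- k = 1: 1.11
- k = 2: 2.22
- k = 5: 5.56

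The values of k are assumptions, because the documents give no count of missing assessments. The shift is an upper limit per row. A subject who already has another related event is in the any-related-event row either way.

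**The case against.** **The table reports the investigator's view.** It is described as "summarized by maximum relationship of each preferred term to study drug (DAA), as assessed by the investigator", whereas 6.1.3 says what the sponsor will consider, so the two might coexist. This does not remove the conflict. The 6.1.3 convention exists for cases where the investigator gave no usable assessment, and its wording is not limited to serious events or expedited reporting. A different convention for tables is possible, but it would need to be declared.

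**The SAP rule is partly protective.** A known reasonable possibility prevails, *unknown* overrides no reasonable possibility, and affected subjects stay visible in their own row. All of this stands. It means that nobody is moved into the unrelated row, but the related row is still lower than under the protocol.

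**Missing assessments should be rare.** Protocol section 6.1 asks the investigator to record severity and relationship for each event, the SAP expects every event to be graded, and data are cleaned before lock. This stands, and the number may be zero. No safety test or threshold depends on the result either.

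**The severity rule can be defended.** The protocol has no rule for a missing grade, and the true maximum is uncertain when one occurrence is ungraded, unless a Grade 5 is known. This makes the severity point the weaker of the two. It does not explain why a known Grade 4 should vanish from a maximum-severity row, since it is a lower bound on that maximum. Both the protocol ("will be counted only once for that term using the most severe grade for the severity grade table") and the SAP's own general sentence call for the highest grade.

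**Conclusion.** The causality conflict is real and undeclared: for the same event, protocol 6.1.3 gives associated and SAP 11.2.2 gives unknown. If any assessments are missing, the related row of the maximum-relationship table can be understated. The drug-related tables can be too, because no mapping rule is stated. The size is at most 1.1 points per affected subject in a row, on the assumption of about 90 treated subjects and with the number affected unknown. The severity point is secondary and limited to the maximum-severity tables, for all and for DAA-related events.

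A reader might infer three stronger conclusions that the documents do not support:

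- *Related events are under-reported, and unknowns drop out of every drug-related summary.* The first depends on assessments being missing. The second is a plausible inference from silence; the SAP does not state it.
- *Severe events are under-reported.* A known Grade 3 or 4 remains in the overview and in the separate Grade 3 or higher tables.
- *The effect could reach 5.6 points.* That needs five affected subjects, a number with no basis in either document. In the severity case it also needs a graded and an ungraded occurrence of the same term in the same subject.

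**What to change.** In SAP section 11.2.2:

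1. Analyse a missing or not-assessable relationship as associated (reasonable possibility) in the maximum-relationship table and in all reasonable-possibility and DAA-related tables. Add a footnote with the number of such events. If the sponsor prefers to keep the *unknown* class, declare the departure in section 12.1 and add the protocol-consistent tabulation as a sensitivity table.
2. In the maximum-severity tables, count the subject at the highest known grade for the term, and use *unknown* only when no occurrence is graded. Add a footnote with the number of subjects who also have an ungraded occurrence.

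The cost is SAP wording and two derivation rules, with no new data. Drug-related and graded counts may be slightly higher. A subject with a low known grade plus an ungraded event will be shown at a lower bound, which is why the second footnote is needed.

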11.2.3 Listing of Adverse Events

The following listings of adverse events will be prepared:

- All serious adverse events (from the time the subject signed the study-specific informed consent through the end of the study),
- Treatment-emergent serious adverse events,
- Treatment-emergent adverse events leading to death,
- Treatment-emergent adverse events leading to discontinuation of study drug,
- Treatment-emergent adverse events leading to study drug interruption.

11.3 Analysis of Laboratory Data

Data collected from the central and local laboratories, including additional laboratory testing due to an SAE, will be used in all analyses.

11.3.1 Variables and Criteria Defining Abnormality

Hematology variables include: hematocrit, hemoglobin, red blood cell (RBC) count, white blood cell (WBC) count, neutrophils, bands, lymphocytes, monocytes, basophils, eosinophils, platelet count, reticulocyte count, prothrombin time (PT), international normalized ratio (INR), and activated partial thromboplastin time (aPTT).

Chemistry variables include: blood urea nitrogen (BUN), creatinine, total bilirubin, direct and indirect bilirubin, alanine aminotransferase (ALT), aspartate aminotransferase (AST), alkaline phosphatase, sodium, potassium, calcium, inorganic phosphorus, cholesterol, total protein, glucose, triglycerides, albumin, chloride, bicarbonate, magnesium, total insulin, gamma-glutamyl transferase (GGT), creatinine clearance (calculated using

Cockcroft-Gault), and estimated glomerular filtration rate (eGFR) calculated using the modification of diet in renal disease (MDRD) equation defined below.

Urinalysis variables include: specific gravity, ketones, pH, protein, blood, glucose, urobilinogen, bilirubin, leukocyte esterase, and microscopic (reflexly performed if other variables are abnormal).

Some of the above laboratory variables are calculated by the laboratory vendor including indirect bilirubin, creatinine clearance, and eGFR by MDRD. The central lab calculates eGFR by MDRD using the following equation, where serum creatinine is measured in mg/dL and age is measured in years:

GFR (mL/min/1.73 m²) = $175 \times (\text{Serum Creatinine})^{-1.154} \times (\text{Age})^{-0.203} \times 1.212$ (if Black) × 0.742 (if Female).

The central lab calculates the estimated creatinine clearance (CrCl) based on the following Cockcroft-Gault formula:

CrCl (mL/min) = $[(140 - age) \times (weight in kg) \times (0.85 \text{ if female})]/[serum creatinine (mg/dL) \times 72].$

11.3.2 Statistical Methods

The baseline value for clinical laboratory tests will be the last non-missing measurement on or before the day of the first dose of study drug. Values on Day 1 must also be before the time of first dose if time is available. The same baseline value will be used for change to Treatment Period visits and change to Post-Treatment Period visits.

Mean changes from baseline to each post-baseline visit, including applicable post-treatment visits, will be summarized. Each protocol-specified laboratory parameter will be summarized with the sample size, baseline mean, visit mean, change from baseline mean, standard deviation, minimum, median, and maximum.

ABT-493/ABT-530

ABT-493/ABT-530 M13-596 – Statistical Analysis Plan Version 1.0 – 27 October 2016

The laboratory parameters defined in Table 8 will be assigned a toxicity grade of 1, 2, 3, or 4. The number and percentage of subjects with a maximum toxicity grade of 1, 2, 3 or 4, will be summarized. The post-baseline value must be in a toxicity grade that is more extreme than the toxicity grade corresponding to the baseline value to be counted. The summary will also include the number and percentage of subjects with a maximum of at least Grade 3 for all laboratory parameters in Table 8. A listing of all relevant laboratory parameters will be provided for each subject who had an increase to Grade 2 or higher for all laboratory variables in Table 8.

Fable 8.Definitions of Toxicity Grades 1, 2, 3, and 4 for Laboratory V	Values
--	--------

Test	Grade 1	Grade 2	Grade 3	Grade 4
ALT/SGPT	$>$ ULN – 3 \times ULN	$> 3 - 5 \times ULN$	> 5 - 20 imes ULN	> 20 imes ULN
AST/SGOT	$>$ ULN – 3 \times ULN	$> 3 - 5 \times ULN$	> 5 - 20 imes ULN	> 20 imes ULN
Alkaline Phosphatase	$>$ ULN – 2.5 \times ULN	$> 2.5 - 5 \times ULN$	> 5 - 20 imes ULN	> 20 imes ULN
Total Bilirubin	$>$ ULN – 1.5 \times ULN	$> 1.5 - 3 \times ULN$	$> 3 - 10 \times ULN$	$> 10 \times ULN$
Hemoglobin	< LLN $-$ 100 g/L	< 100 - 80 g/L	< 80 g/L	
Absolute Neutrophil Count	$<$ LLN $- 1.5 \times 10^9$ /L	$< 1.5 - 1.0 \times 10^9 / L$	$< 1.0 - 0.5 \times 10^9 / L$	$< 0.5 \times 10^{9}/L$
Platelet count	$< LLN - 75.0 \times 10^9 / L$	$<75.0-50.0\times 10^9\!/L$	$< 50.0 - 25.0 \times 10^9 \! / \! L$	$<25.0\times10^9/L$
INR	$> 1 - 1.5 \times ULN$	$> 1.5 - 2.5 \times ULN$	$> 2.5 \times ULN$	
Creatinine clearance	< LLN - 60 mL/min	< 60 - 30 mL/min	< 30 - 15 mL/min	< 15 mL/min
Creatinine	$>$ ULN – 1.5 \times ULN	$> 1.5 - 3 \times ULN$	$> 3 - 6 \times ULN$	$> 6 \times ULN$
Albumin	< LLN $-$ 30 g/dL	< 30 - 20 g/L	< 20 g/L	

Assessment of Hepatic Laboratory Parameters

The number and percentage of subjects with maximum on-treatment lab values meeting the following criteria will be summarized:

- ALT \geq 3 × ULN and total bilirubin \geq 2 × ULN;
- ALT \ge 3 × ULN and total bilirubin < 2 × ULN;
 - ALT > 5 × ULN and total bilirubin < 2 × ULN;
- ALT < $3 \times$ ULN and total bilirubin $\ge 2 \times$ ULN.

ABT-493/ABT-530 M12 506 Statistic

ABT-493/ABT-530 M13-596 – Statistical Analysis Plan Version 1.0 – 27 October 2016

The maximum ratio relative to the ULN will be used to determine if subjects meet the criteria listed above. The ALT and total bilirubin values do not need to be concurrent in order to meet the defined criteria. For ALT, the post-baseline value must represent an increase from the first nadir (including baseline) to be counted. First nadir is defined as the last value prior to the first increase. For total bilirubin, a subject will be counted if the post-baseline laboratory value meets the above criteria regardless of the baseline laboratory value (i.e., the post-baseline laboratory value does not need to be worse than the baseline laboratory value).

A listing of all ALT, AST, total, indirect and direct bilirubin, ratio of direct to total bilirubin, and alkaline phosphatase values will be provided for each subject who met any of the criteria defined above. The listings will be reviewed to assess bilirubin (e.g., mixed or direct predominance) and temporal relationships for subjects with $ALT \ge 3 \times ULN$ and total bilirubin $\ge 2 \times ULN$.

The number and percentage of subjects with post-baseline values during the Treatment Period meeting the following criteria will be summarized:

- ALT > 5 × ULN and \geq 2 × baseline;
- AST > 5 × ULN and \geq 2 × baseline;
- Total bilirubin $\geq 2.0 \times ULN$ and > baseline.

As noted above, a post-baseline value must be more extreme than the baseline value to be considered. A separate listing will be provided that presents all lab values for the subjects meeting any of these criteria during treatment.

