Blood samples for serum chemistry tests should be collected following a minimum 8-hour fast prior to study drug intake (with the exception of the Screening Visit, which may be non-fasting). Subjects whose visits occur prior to the morning dose of study drug should be instructed to fast after midnight until the blood sample is collected in the morning and thereafter take their study medications with food. Subjects whose visits occur following the morning dose of study drug should be instructed to fast after breakfast until the study visit occurs. At the Study Day 1 visit, a fasting blood sample should be collected prior to the first dose of study drug. Blood samples should still be drawn if the subject did not fast for at least 8 hours. Fasting or non-fasting status will be recorded in the source documents and on the laboratory requisition. The baseline laboratory test results for

clinical assessment for a particular test will be defined as the last measurement prior to the initial dose of study drug.

A central laboratory will be utilized to process and provide results for all other clinical laboratory tests.

Instructions regarding the collection, processing, and shipping of these samples will be provided by the central laboratory chosen for this study. The certified laboratory chosen for this study is Covance. Samples will be sent to the following addresses:

Covance [name] (For sites in North America)

Covance [name] (For sites in Europe)

Covance (Asia) Pte Ltd
[name]
[name]
[name]
(For sites in Asia Pacific)

[figure not shown]

Table 2. Clinical Laboratory Tests

Hematology	Clinical Chemistry	Other Tests	
Hematocrit	Blood Urea Nitrogen (BUN)	HBsAg ^c	
Hemoglobin	Creatinine Anti-HCV Ab ^c		
Red Blood Cell (RBC) count	Direct and indirect bilirubin	Anti-HIV Ab ^c	
White Blood Cell (WBC) count	Total bilirubin	Opiates ^c	
Neutrophils	Albumin	Barbiturates ^c	
Bands	Aspartate aminotransferase (AST)	Amphetamines ^c	
Lymphocytes	Alanine aminotransferase (ALT)	Cocaine ^c	
Monocytes	Alkaline phosphatase	Benzodiazepines ^c	
Basophils	Calcium	Alcohol ^c	
Eosinophils	Inorganic phosphate	Phencyclidine ^c	
Platelet count (estimate not	Sodium	Propoxyphene ^c	
acceptable)	Potassium	Methadone ^c	
Reticulocyte count	Cholesterol	Urine and Serum	
Prothrombin Time/INR	Low Density Lipoproteins (LDL) _L ^{a,b}	Human Chorionic	

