5.5.4 Selection and Timing of Dose for Each Subject

Study drug dosing will be initiated at the Study Day 1 Visit. ABT-493/ABT-530 will be dosed every morning with food. Study drug and allowed immunosuppressants (cyclosporine, everolimus, sirolimus, tacrolimus, azathioprine, MMF, and mycophenolic acid) should be taken together with food at approximately the same times in the morning every day. This is important as taking the DAAs in combination with the immunosuppressants at different times can significantly alter the level of the immunosuppressants.

[figure not shown]
Selection of the doses for this study is discussed in Section 5.5.4.

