- Baseline eGFR (< $60, \ge 60$ to < $90, \ge 90$ mL/min/1.73 m²);
- Baseline fibrosis stage (equivalent to Metavir F0 F1, F2, F3, or F4 [if applicable]);
- Baseline platelet count (< 90 or \ge 90 × 10⁹/L);
- Baseline albumin (< 35 or \geq 35 g/L);
- History of diabetes (yes/no);
- History of bleeding disorders (yes/no);
- History of depression or bipolar disorder (yes/no);
- History of cardiovascular disease (yes/no);
- Type of transplant (liver or kidney),
 - For renal transplant subjects, prior dialysis type (hemodialysis, peritoneal dialysis, other, or not done);
- Donor type (living or deceased);
- Immunosuppressant medication (Tacrolimus, Cyclosporine, other);
- Injection drug user (yes, within last 12 months; yes, more than 12 months ago; or no);
- Subject on stable opiate substitution (yes/no);

- Tobacco use (user, ex-user, or non-user);
- Alcohol use (drinker, ex-drinker, or non-drinker);
- Concomitant use of Proton Pump Inhibitors (PPIs).

Summaries of baseline resistance are described in Section 10.8.

Any concomitant medication coded to the WHO Drug Dictionary ATC code of A02BC will be counted as a PPI.

If the IL28B genotype result is not available from a sample collected on Day 1, then a result available from a sample collected at any time during the study will be used to summarize IL28B genotype. IL28B rs12979860 will be resulted as C/C, C/T, or T/T by the central laboratory.

HOMA-IR is defined as fasting glucose (mmol/L) \times fasting insulin (μ IU/mL) \div 22.5. Subjects who do not have concurrent fasting glucose and fasting insulin values at baseline will be excluded from the summary of baseline HOMA-IR.

Baseline fibrosis stage is defined for subjects with non-missing liver biopsy scores, FibroScan scores, or FibroTest scores. Only one score will be used to categorize each subject even if a subject has more than one score recorded. If a biopsy score is present, then it will be used to categorize the subject, regardless of the FibroScan/FibroTest score. Similarly, if a FibroScan score is present along with a FibroTest score, then the FibroScan score will be used to categorize the subject. If biopsy and FibroScan scores are not present and more than one FibroTest result is available, then the baseline FibroTest result (i.e., last non-missing FibroTest result on or before Day 1) will be used to categorize the subject. Subjects will be categorized as F0 - F1, F2, F3, or F4 according to Table 4.

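### SAP 11.3.2 does not use the recorded fasting status, so mean changes in glucose and triglycerides can mix fasting and fed samples

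*SAP*

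**What the plan says.** **Collection (Protocol 5.3.1.1, Clinical Laboratory Tests).** The general rule is "Blood samples for serum chemistry tests should be collected following a minimum 8-hour fast prior to study drug intake"; only the Screening Visit may be non-fasting. For baseline, "At the Study Day 1 visit, a fasting blood sample should be collected prior to the first dose of study drug". Later visits fall into two cases. Subjects seen before the morning dose "should be instructed to fast after midnight until the blood sample is collected in the morning". For the others, "Subjects whose visits occur following the morning dose of study drug should be instructed to fast after breakfast until the study visit occurs"; that sentence sets no minimum length. There is also a fallback: "Blood samples should still be drawn if the subject did not fast for at least 8 hours". Fasting status goes into the source documents and onto the laboratory requisition.

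**Dosing (Protocol 5.5.4).** "ABT-493/ABT-530 will be dosed every morning with food", so a visit after the dose follows a meal.

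**Analysis (SAP 11.3.1, 11.3.2 and 6.2).** Glucose and triglycerides are listed as chemistry variables. For every parameter, "Each protocol-specified laboratory parameter will be summarized with the sample size, baseline mean, visit mean, change from baseline mean", followed by measures of spread, at each post-baseline visit including applicable post-treatment visits. Baseline is the last non-missing value up to first dose. Neither the baseline rule nor the visit windows refer to fasting. SAP 11.3 also brings local-laboratory and SAE-related results into all analyses.

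**Where the SAP does use fasting (SAP 7.1).** "Subjects who do not have concurrent fasting glucose and fasting insulin values at baseline will be excluded from the summary of baseline HOMA-IR".

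**The concern.** Glucose and triglycerides respond to meals. The SAP accepts this for baseline HOMA-IR, where it requires fasting glucose, but applies no such condition when it summarizes change in glucose. If baseline samples are mostly fasting and some later ones are not, part of the mean change reflects breakfast.

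Safety is part of the primary objective, and there is no control arm in which the same meal effect would appear and cancel. Little else collected on treatment would help to interpret a rise: under Protocol Table 2, hemoglobin A1c is measured only at Screening, and LDL and HDL only at Baseline. A reader of the study report could take a modest mean rise as a drug effect, or dismiss a real one as a meal effect, without the means to tell which.

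**Working it through.** The plan states no figure on this point, so there is nothing to reproduce. The check sets the rules side by side and then gives an illustrative size.

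**1. Can fed samples enter?**

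| Sample | Protocol instruction | Used in SAP 11.3.2? |
|---|---|---|
| Screening | May be non-fasting | Yes, as baseline if no later pre-dose value exists |
| Day 1, pre-dose | Fasting; still drawn if not fasted 8 hours | Yes, as baseline |
| On treatment, before morning dose | Fast after midnight | Yes |
| On treatment, after morning dose | Fast since breakfast; still drawn if under 8 hours | Yes |
| Post-treatment | General 8-hour rule; still drawn if not met | Yes |

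Fed values can enter on either side of the change. As an example, after a breakfast assumed to be at 08:00, the 8-hour rule is met only from 16:00 (08:00 + 8 h). A post-dose visit earlier in the day gives a sample that falls short of the rule but is still drawn and analyzed.

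**2. Direction.** Let f_b be the share of baseline samples that are fed, f_v the share at a visit, and m the mean fed-minus-fasting difference. With no true change,

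expected mean change = (f_v − f_b) × m.

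If Day 1 instructions are followed, f_b is near 0 and the shift is upward or nil. If f_b exceeds f_v, the sign reverses: with f_b = 0.10, f_v = 0 and glucose m = 0.3 to 2.0 mmol/L, the shift is −0.03 to −0.20 mmol/L.

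**3. Size, with f_b = 0.** The documents give neither f_v nor m. The following ranges are assumptions: f_v = 0 to 0.50; m = 0.3 to 2.0 mmol/L for glucose and 0.2 to 1.0 mmol/L for triglycerides.

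| f_v | Glucose shift (mmol/L) | Triglyceride shift (mmol/L) |
|---|---|---|
| 0 | 0 | 0 |
| 0.10 | 0.03 to 0.20 | 0.02 to 0.10 |
| 0.25 | 0.075 to 0.50 | 0.05 to 0.25 |
| 0.50 | 0.15 to 1.0 | 0.10 to 0.50 |

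**4. Scale.** With the planned n of 90, the 95% half-width of a mean change is 1.96 × SD / √90. An assumed glucose SD of 1.5 mmol/L gives 0.31; an SD of 2.5 gives 0.52. The glucose shift could be far below the precision of the mean or exceed it.

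**5. After the fix.** With only fasting samples at both time points, f_b = f_v = 0 and the shift is 0 for any m.

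**6. Reach.** Neither parameter is in SAP Table 8, so toxicity grades do not change. SVR12 and the hepatic criteria do not use them.

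**The case against.** The strongest reply is that the protocol deals with this at collection. The 8-hour rule covers every visit except Screening, and drawing blood after a shorter fast is a fallback so that safety samples are not lost.

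The schedule also favours fasted visits. Appendix C pairs chemistry with cyclosporine, tacrolimus, everolimus or sirolimus monitoring at every treatment visit. Section 5.3.1.1 describes those draws as trough samples, and sections 5.2.3.2 and 5.5.4 have the immunosuppressant taken with study drug in the morning with food. A morning trough draw thus comes before both drug and breakfast. Subjects in optional intensive PK sampling have a pre-dose draw at Week 4 as well.

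This lowers the likely fed share but does not make it zero. Trough sampling covers only those four drugs, routine PK samples are taken without regard to dosing time (section 5.3.2.1), and the protocol writes explicit instructions for visits after the dose.

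Two stronger readings are tempting. A reader might infer that these means are biased upward at every visit after Day 1. The documents do not support that: the post-dose instruction cannot apply at post-treatment visits, where no study drug is taken, and an unfasted baseline can turn the bias the other way. A reader might also infer that mean change is the only planned look at these two parameters. Protocol 8.1.5.2 also plans normal-range shift summaries, SAP 6.2 has a rule for such shifts, and SAP 12.1 does not list them as dropped. They carry the same mixing, so a fix to the means alone would be incomplete.

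**Conclusion.** The point holds as a minor gap in the SAP. Fasting status is to be recorded and is treated as material for baseline HOMA-IR, but it is not used where glucose and triglycerides are compared over time. The mean changes can mix fasting and fed samples; the documents do not show that they will do so to a material degree.

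Under the assumed ranges with a fasting baseline and at least 10% fed samples, the shift is 0.03 to 1.0 mmol/L for glucose and 0.02 to 0.5 mmol/L for triglycerides. These are arithmetic on assumptions, not estimates for this trial. With few fed samples the effect is negligible. The summaries are descriptive, with no test or decision rule attached. The case for acting is that the remedy is cheap and removes an ambiguity that a single-arm design cannot resolve afterwards.

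**What to change.** In SAP 11.3.2, add that by-visit and change-from-baseline summaries of glucose and triglycerides use only samples recorded as fasting at both baseline and the visit, with the remaining results in a separate row. Apply the same rule to any normal-range shift summaries of these two parameters under Protocol 8.1.5.2.

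Confirm that the fasting status on the requisition is transferred to the analysis database. The protocol names only the source documents and the requisition, although the HOMA-IR rule already needs this information at baseline.

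The cost is a sentence or two in the SAP, a data-transfer check, and a smaller n for these parameters at some visits. No change to sample collection is needed.
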